1. PROTOCOL SUMMARY

1.1. Synopsis

Protocol Title: A Phase 2, Open-label Study to Assess Copper and Molybdenum Balance in Participants with Wilson Disease Treated with ALXN1840

Short Title: Copper and Molybdenum Balance in Participants with Wilson Disease Treated with ALXN1840

Rationale:

The principal aim of this exploratory study is to investigate the effects of ALXN1840 on copper balance in participants with Wilson disease (WD). The study will specifically evaluate the effects of 2 different ALXN1840 doses as well as the duration of treatment on copper balance to further elucidate the dose response of “decoppering” versus “maintenance” dose in participants with WD.

The secondary aim of the study is to characterize the steady-state absorption, distribution, metabolism, and excretion (ADME; mass balance) of total molybdenum which is a surrogate measure of ALXN1840 disposition in participants with WD.

ALXN1840 contains the active anion tetrathiomolybdate and has been shown to cause negative copper balance when administered to healthy animals as well as decopper the liver in animal models of WD. In Study WTX101-201, which assessed the safety and efficacy of ALXN1840 in participants with WD, ALXN1840 demonstrated enhanced copper control as measured by reduced plasma non-ceruloplasmin-bound copper (NCC) corrected (NCC_{corrected}) for the stable tetrathiomolybdate- copper -albumin tripartite complex (TPC).

Depletion of copper by ALXN1840 has been shown to occur primarily through fecal elimination in both healthy and WD animal models. In this study, copper balance will be calculated as the difference between measured copper input in food and drink and measured copper output in urine and feces. This method is classically considered the most objective measure of decoppering ability with a decoppering agent able to drive a net negative copper balance.

As part of the secondary objective, to confirm that ALXN1840 steady state is adequately characterized by the plasma pharmacokinetics (PK), a molybdenum mass balance assessment will be performed at predicted steady state for the 15 mg/day and 30 mg/day doses: if steady state is achieved, molybdenum(out) will equal molybdenum(in). This approach may also detect potential accumulation in the liver or other tissues of participants with WD.

Objectives and Endpoints

Objectives	Endpoints

Primary Assess net copper balance with daily repeat-dose ALXN1840 treatment (15 mg and 30 mg) in participants with Wilson disease (WD)
	Mean daily copper balance where copper balance is measured by the calculated difference between copper intake (in food and drink) and copper output (in feces and urine) during ALXN1840 accumulation and steady-state periods for each dose

Secondary Assess change in copper balance in response to ALXN1840 15 mg/day and 30 mg/day during ALXN1840 accumulation and at steady state periods versus the pretreatment baseline in participants with WD
	Change in mean daily copper balance as measured by the calculated difference between copper intake (in food and drink) and copper output (in feces and urine) from pretreatment baseline (Days -4 through -1) and ALXN1840 accumulation and steady-state periods for each dose
Investigate the effect of ALXN1840 (15 mg/day and 30 mg/day) on the disposition of copper in participants with WD	Copper quantified in food, drink, feces, and urine, including plasma total and labile bound copper (LBC) during ALXN1840 accumulation and steady-state periods for each dose
Investigate the effect of ALXN1840 on the disposition of molybdenum at steady state at 15 mg/day and 30 mg/day in participants with WD	Molybdenum quantified in food, drink, feces, and urine, plasma total molybdenum at ALXN1840 steady state
Assess steady-state total molybdenum balance as a measure of ALXN1840 15 mg/day and 30 mg/day in participants with WD	Mean daily molybdenum balance as demonstrated through measurement of molybdenum intake (in food, drink and ALXN1840), and molybdenum output (feces and urine) representing ALXN1840 steady state
Assess accumulation of molybdenum with ALXN1840 treatment at 15 mg/day and 30 mg/day in participants with WD	Accumulation of molybdenum as determined by molybdenum balance
Determine the steady-state plasma pharmacokinetic (PK) of total molybdenum and plasma ultrafiltrate (PUF) molybdenum (as surrogate measures of ALXN1840, 15 mg and 30 mg) in participants with WD	PK parameters for plasma total and PUF-molybdenum

Safety Evaluate the safety and tolerability of repeated-dose administration of ALXN1840 15 mg/day and 30 mg/day in participants with WD
	
Safety parameters:
 
 • Treatment emergent adverse events (TEAEs)/serious adverse events (SAEs) • Clinical laboratory assessments (serum chemistry, hematology, coagulation, and urinalysis) • Physical examinations • Heart rate, intervals (PR, QRS, QT and QTc), and clinically significant electrocardiogram (ECG) findings as determined by triplicate 12-lead ECG • Vital sign assessments (blood pressure and heart rate)

Exploratory Determine dose response of ALXN1840 15 mg/day and 30 mg/day for copper balance in participants with WD
	Assess dose response of ALXN1840 on copper balance focusing on copper balance
Determine the effect of treatment duration on copper balance in participants with WD	Determine the effect of time following initiation of ALXN1840 treatment on copper balance
Assess the effects of ALXN1840 on ceruloplasmin, ceruloplasmin-bound copper LBC profiles in plasma in participants with WD	Ceruloplasmin, ceruloplasmin-bound copper, and LBC: Change in ceruloplasmin at Days 1, 8, 25, 29, 36, and Day 39 compared with predose

Objectives	Endpoints
Assess dose proportionality at steady state of doses of ALXN1840 15 mg/day and 30 mg/day in participants with WD	Based on PK parameters
Assess effects ALXN1840 on copper:molybdenum ratio in plasma at steady state in participants with WD	Measure plasma copper:molybdenum ratios at steady state compared with predose
Assess the effects of repeat-dose ALXN1840 on copper:molybdenum ratio in urine and feces in participants with WD	Mean daily copper:molybdenum ratio in urine and feces at steady state compared with predose baseline

Note: The accumulation period refers to time from initiation of ALXN1840 (Day 1) to expected steady state at Day 10, based on 5 times the half-life of 2 days.

Overall Design

This is a single-arm, open-label, repeat-dose study to evaluate the effects of ALXN1840 administration on copper balance in participants with WD. The safety and tolerability of ALXN1840 in participants with WD will also be assessed. ALXN1840 PK in plasma as measured via total molybdenum and plasma ultrafiltrate (PUF) molybdenum will be determined after repeated dosing along with total molybdenum mass balance at steady state.

Disclosure Statement: This is an open-label, 3-period study with 1 arm.

Number of Participants:

The sample size will be approximately 10 participants which will allow a general characterization of copper balance in response to ALXN1840.

Note: “Enrolled” means all participants who sign the informed consent form (ICF), are eligible for the study, and are registered on Day -7 when participants are assigned a participant number.

Intervention Groups and Duration:

Treatment-experienced (which includes standard of care therapies or ALXN1840) and treatment-naïve participants are eligible for this study. Following screening and enrollment, participants will have a Run-in Period to support diet equilibration (Day -7 through Day -5) and measurement of pretreatment copper and molybdenum balance (Day -4 through Day -1). Following the Run-in Period, participants will be administered ALXN1840 at 15 mg/day for a treatment period of approximately 28 days followed by titration up to 30 mg/day on Day 29. Before titration to 30 mg/day, the Safety Review Committee (SRC) will review available safety data through Day 23 for each participant.

Participants will have intake and output collection periods from Day -4 through Day -1, from Day 1 through Day 8 (initial 15 mg/day collection period), and Day 25 through Day 39. The collection periods will support an assessment of both copper and molybdenum balance (as a measure of ALXN1840 ADME) at the 15 mg/day and 30 mg/day doses and will allow assessment of the effects of duration of treatment on copper elimination and copper balance.

Participants may be discharged from the clinical research unit (CRU) on Day 9 to return on Day 22 or Day 23 (predose); all procedures will start on Day 23. To ensure flexibility, the Outpatient Period during Treatment Period 1 may be extended up to an additional 14 days with Investigator approval. In this situation, participants will be given additional investigational product to support daily dosing throughout the Outpatient Period. In such cases, the actual Outpatient Period

[figure not shown]
duration will be recorded and the participant will continue Inpatient Period 2 at Day 23. During the Outpatient Period, participants will use SMS text messaging to confirm study intervention administration. At the CRU's discretion, participants may remain in the CRU during the outpatient period for safety or to maintain the integrity of the conduct of the study.

Safety Review Committee:

A Safety Review Committee (SRC), composed of a minimum of the Investigator, Alexion Medical Monitor, and Alexion Safety Physician, will meet at the end of 15 mg/day dosing to confirm proceeding to 30 mg/day and as necessary based on any emerging safety concerns.

1.2. Schema

Figure 1: Study Schematic

- Participants eligible for the study will be enrolled on Day -7 and initiated on a copper- and molybdenum-controlled diet, which will be continued during Treatment Period 1 and Treatment Period 2 when in the CRU, through Day 39.
- Participants will be admitted to the CRU for Treatment Period 1 on Day -8 and may be discharged on Day 9 or remain in the CRU for their own safety or to maintain the integrity of the conduct of the study. Participants who are discharged will be re-admitted on Day 22 or Day 23 for Treatment Period 2 and will remain in house until Day 40. To ensure flexibility, the Outpatient Period may be extended up to an additional 14 days with Investigator approval. In this situation, participants will be given additional investigational product to support daily dosing throughout the Outpatient Period. In such cases, the actual Outpatient Period duration will be recorded and the participant will continue Inpatient Period 2 at Day 23.
- Participants will be administered ALXN1840 at a dose of 15 mg/day on Day 1 through Day 28 and then increase to 30 mg/day on Day 29 through Day 39. During the Outpatient Period, participants will use SMS text messaging to confirm study intervention administration.
- Participants will have 3 intake and output collection periods including:
 - Baseline Day -4 through Day -1
 - Day 1 through Day 8 (I/O for 15 mg)
 - Day 25 through Day 39 (Days 25 through 28, I/O for 15 mg; Days 29 through 39, I/O for 30 mg)
- During these periods all intake (including food and drink) and output (including urine and feces) will be collected and assessed for copper and molybdenum.
- Blood sampling for PK/PD will be as follows:
 - PK/PD collection (24-hour): Days 1, 25, 29, and 39
 - Pre-dose PK/PD sampling days: Days 4 - 7, Days 26 - 28, Days 30 - 38
 - End of Study Visit Day 54 +/- 2 days

Abbreviations: AP = accumulation period; CRU = clinical research unit; EOS = End of Study; I/O = input/output; PD = pharmacodynamic; PK = pharmacokinetic; SS = steady state.

1.3. Schedule of Activities (SoA)

Table 1: Schedule of Activities

Study Procedures	Screening ^a		C-I ^b																		UNS ^d	EOS or ET ^e			
	Screening	C-I	C-I	Inpatient Period 1							OP ^c	Inpatient Period 2													
Days	-42 to -9	-21	-8	-7	-6 through -5	-4 through -1	1	2-3	4-7	8	9	10-22	23	24	25	26-28	29	30-35	36	37-38	39	40		EOS Day 54+/-2	
Eligibility																									
Informed consent	X																								
Admit to unit			X										X												
Discharge from unit ^f											X											X			
Outpatient visit or phone call												X ^g													
Inclusion/exclusion	X		X				X																		
Discuss/document contraception	X		X								X														X
Follicle-stimulating hormone (post-menopausal females only ^h)	X																								
Alcohol test	X		X																						
Urine drug screen	X		X																						
HIV, hepatitis B and C screen	X																								
Study Administration																									
Medical history/demographics ⁱ	X																								
WD history ^j	X																								
Prior WD treatment ^j	X						X																		
Physical examination ^k	X		X									X													X
Height ^l , weight, and BMI	X		X									X										X			
Enrollment																									
Enrollment/inclusion				X																					
Discontinue chelation therapy						X																			→
Discontinue zinc therapy		X																							→
Administration of Study Intervention^m																									
ALXN1840 15 mg/day							X	X	X	X	X	X	X	X	X	X									
ALXN1840 30 mg/day																	X	X	X	X	X				
Study intervention compliance											X ⁿ	X													
PK/PD Analyses^o																									
Blood sampling for PK: Plasma total Mo and PUF-Mo							X ^p	X						X ^p	X	X ^p	X	X	X	X	X ^p	X			

Study Procedures	Screening ^a		C-I ^b																		UNS ^d	EOS or ET ^e			
	Screening		C-I	Inpatient Period 1							OP ^c	Inpatient Period 2													
Days	-42 to -9	-21	-8	-7	-6 through -5	-4 through -1	1	2-3	4-7	8	9	10-22	23	24	25	26-28	29	30-35	36	37-38	39	40		EOS Day 54+/-2	
PD: Plasma total and PUF-Cu, LBC, ceruloplasmin, ceruloplasmin-bound Cu																									
Safety Assessments / Laboratory Analyses																									
Chemistry ^g , hematology, Coagulation	X		X			X ^r				X		X ^g	X			X ^r		X				X		X	
Urinalysis	X		X							X		X ^g	X			X						X		X	
Urine/serum pregnancy test ^s	X		X									X												X	
Retained serum sample (safety) ^f				X																					
Vitals sign measurements ^h	X			X			X				X		X									X		X	
12-lead ECG (triplicate)	X			X			X				X		X									X		X	
Adverse events	X		X	X	X	X	X	X	X	X	X	X	X	X	X	X	X	X	X	X	X	X	X	X	
Balance assessments																									
Cu/Mo-controlled meals ^v				X	X	X	X	X	X	X			X	X	X	X	X	X	X	X	X	X			
Light exercise regimen				X	X	X	X	X	X	X		X	X	X	X	X	X	X	X	X	X	X			
Urination and bowel movement monitoring, menstruation check ^s						X	X	X	X	X					X	X	X	X	X	X	X	X			
24-hour urine for Cu and Mo ^w						X	X	X	X	X					X	X	X	X	X	X	X	X			
Feces for Cu and Mo ^x						X	X	X	X	X					X	X	X	X	X	X	X	X			
Other																									
Concomitant medication and non-pharmacologic therapy/procedure	X		X	X	X	X	X	X	X	X	X	X	X	X	X	X	X	X	X	X	X	X		X	

^a Within 42 days of ALXN1840 administration. Details of procedures that may be performed by sites designated as “screening sites” (only in the US) are detailed in Section 8.

^b Participants will be admitted to the clinical research unit (CRU) at least 10 hours prior to enrollment and initiation of copper- and molybdenum-controlled diet.

^c At the CRU’s discretion, participants may remain in the CRU or be readmitted on Day 22 with all procedures starting on Day 23.

^d Unscheduled study visits may occur at any time during the study and may include any study procedure as deemed necessary by the Investigator.

^e Participants are required to return to the CRU Day 54+/-2; participants will be discontinued from ALXN1840 medication by their physician at the latest by the Day 54 follow-up.

^f Discharge from the unit may occur after completion of all procedures on Day 9 and on Day 40 and after the Investigator has reviewed all safety assessment (including safety laboratory tests) and confirmed that the participant is appropriate for discharge.

^g A single outpatient visit or phone call and safety laboratory assessment should occur between Day 14 and Day 18. A phone call may take place on a different day than the blood draw within the Day 14 through Day 18 period.

^h If needed to confirm menopause.

- ⁱ Parameters include age and sex. Race and ethnicity will be collected where permitted by local regulations.
- ^j Wilson disease history will include diagnosis date, method of diagnosis, history of cirrhosis, details of any previous liver biopsies performed, and treatment received.
- ^k A full physical examination will be performed at Screening, at check-in for the study, and at the End of the study/Early Termination Visit. A physical examination should also be performed on any participants with ongoing adverse events prior to discharge from the unit. Otherwise, a symptom-driven physical examination may be performed at other times, at the Principal Investigator's discretion.
- ^l Height at screening only.
- ^m While in the CRU, study intervention will be administered after an overnight fast (ie, at least 10 hours) at the same time every morning; drug is to be administered with 240 mL of water and meals should be delayed a minimum of 2 hours after dosing. As an outpatient, participants are expected to take ALXN1840 at approximately the same time daily (+/-1 hour). Participants should take the medication with a glass of water on an empty stomach; meals should be delayed a minimum of 2 hours after dosing.
- ⁿ During the outpatient period, participants will use SMS text messaging to confirm study intervention administration.
- ^o Blood sampling for PK/PD will occur before ALXN1840 administration and represents a predose trough. See [Table 2](#) for PK/PD sampling on Days 1, 25, 29, and 39.
- ^p PK/PD collection will include timepoints described in the schedule of PK/PD assessment for Days 1, 25, 29, and 39 ([Table 2](#)).
- ^q Samples for serum chemistry will be obtained following a fast of at least 8 hours at the Screening Visit and at check-in. In case of rechecks, and postdose serum chemistry, participants may not have fasted for 6 or 8 hours before the serum chemistry sample is taken.
- ^r Laboratory assessment including chemistry, hematology, and coagulation parameters should be performed on Days -8, -1, 8, 23, and 28 only.
- ^s Menstruation check is for women only; women of childbearing potential should only be enrolled after a negative serum pregnancy test result at Screening. Additional urine pregnancy testing will be standard for the protocol unless serum testing is required by site policies, local regulation, or Institutional Review Boards (IRBs)/Independent Ethics Committees (IECs) (Section 10.2). In addition to pregnancy tests detailed at the visits in the SoA, females of childbearing potential will be required to perform urine pregnancy tests at least every 4 weeks at their home or the study site throughout their time in the study.
- ^t A single 15 mL serum sample will be retained for evaluation in the event of an unexpected safety finding; retained samples may be destroyed after completion of the clinical study report.
- ^u Vital signs measurements and ECGs should be performed predose, unless otherwise specified. Vitals signs include body temperature, heart rate, respiratory rate, and systolic and diastolic blood pressure.
- ^v Copper- and molybdenum-controlled diet will be initiated after registration/inclusion. Participants will remain on a copper/molybdenum controlled diet throughout both the inpatient Period 1 (Day -8 to Day 9) and inpatient Period 2 (Day 23 to Day 40); during this time participants will be strongly encouraged to complete all meals. While not in the CRU, participants will be encouraged to adhere to their usual copper-controlled diet.
- ^w For each input/output balance period, 24-hour urine samples are to be collected for measurement of copper and molybdenum.
- ^x For fecal samples, each individual sample will be independently collected with record of date, time, and weight of the sample.
- Abbreviations: AE = adverse event; BMI = body mass index; C-I = check-in; Cu = copper; D = day; ECG = electrocardiogram; EOS/ET = End of Study or Early Termination; HIV = human immunodeficiency virus; HR = heart rate; LBC = labile bound copper; Mo = molybdenum; OP = outpatient; PD = pharmacodynamic; PK = pharmacokinetics; PUF = plasma ultrafiltrate; UNS = unscheduled; WD = Wilson disease.

Table 2: Schedule of Pharmacokinetic and Pharmacodynamic Assessments on Days 1, 25, 29, and 39

Time point (hours) ^a	-0.5	0	1	2	3	4	5	6	8	12	24
Blood sampling for PK: Plasma total Mo and PUF-Mo PD: Plasma total and PUF-Cu, LBC, ceruloplasmin, ceruloplasmin-bound Cu	X			X		X	X	X	X	X	X ^b

Note: Windows for PK/PD time points will be defined as $\pm 10\%$ of the nominal time point. On Days 1 and 39, triplicate 12-lead ECG will be collected at 4 hours postdose. When multiple procedures are scheduled to occur at the same time, the following order of events should be strictly adhered to whenever possible: ECG, vital signs, blood sampling (eg, for PK/PD), study intervention administration, and meal.

^a Time points are relative to dosing (0 hours).

^b Hour 24 PK/PD sampling is to occur just prior to the next-day dose of ALXN1840.

Abbreviations: Cu = copper; LBC = labile bound copper; Mo = molybdenum; PD = pharmacodynamic; PK = pharmacokinetic; PUF = plasma ultrafiltrate.

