2.3.1. Risk Assessment

Details of the potential risks and mitigation strategy are provided in [Table 3](#).

Table 3: Potential Risks and Mitigation Strategy

Potential Risk of Clinical Significance	Summary of Data/Rationale for Risk	Mitigation Strategy
ALXN1840		
Dose-dependent elevations in transaminases (ALT and AST)	Generally mild to moderate in severity, asymptomatic and reversible with dose adjustments were reported, usually after 3 - 6 weeks of treatment. Results obtained from studies of ALXN1840 and ammonium tetrathiomolybdate in participants with WD; see the IB.	Regular monitoring of liver function tests. Dose modification or discontinuation (Section 6.6).
Anemia	Anemia has been observed in participants with WD, attributed to overtreatment and resultant copper depletion; see the IB.	Monitoring complete blood count. Dose modification or discontinuation (Section 6.6).
Low white blood cell count (leukopenia, bone marrow toxicity)	Leukopenia and bone marrow toxicity (myelosuppression) have been observed in participants with WD, attributed to overtreatment and resultant copper depletion. Results obtained from studies of ALXN1840 and ammonium tetrathiomolybdate in participants with WD; see the IB.	Monitoring of complete blood count. Dose modification or discontinuation (Section 6.6).
Neurological dysfunction	Neurological worsening may occur due to copper mobilization. Peripheral neuropathy may be seen with over decoppering; however, symptoms such as myelosuppression is typically seen earlier.	Regular monitoring for neurologic adverse events. Dose modification or discontinuation (Section 6.6).
Study Procedures		
Risks associated with the study design and procedures	Participants will undergo repeated blood draws to measure the PK of the study intervention and metabolism. Blood draws may result in ecchymosis, redness, and minor pain to the site. On rare occasion, infection or thrombophlebitis can occur.	Blood draws are optimized for PK. A cannula may be placed to minimize needle sticks; however, a catheter may not be left in place for longer than 72 hours and should be flushed a minimum of every 8 hours.

Abbreviations: ALT = alanine aminotransferase; AST = aspartate aminotransferase; IB = Investigator's Brochure; PK = pharmacokinetics; WD = Wilson disease.

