Participants may be discharged from the CRU on Day 9 and return on Day 22 or Day 23 (predose); all procedures will start on Day 23. To ensure flexibility, the Outpatient Period during Treatment Period 1 may be extended up to an additional 14 days with Investigator approval. In this situation, participants will be given additional investigational product to support daily dosing throughout the Outpatient Period. In such cases, the actual Outpatient Period duration will be recorded and the participant will continue Inpatient Period 2 at Day 23. During the Outpatient Period, participants will use SMS text messaging to confirm study intervention administration. At the CRU's discretion, participants may remain in the CRU during the outpatient period for safety or to maintain the integrity of the conduct of the study.

Blood sampling for PK/pharmacodynamic (PD) will occur over the 24-hour dosing period on Days 1, 25, 29, and 39. Predose PK samples will be collected at all time points during the intake and output collection period to help characterize PK during accumulation (Days 1 through 9 for 15 mg and Days 31 through 35 for 30 mg) and at steady state (Days 25 through 28 for 15 mg and Days 36 through 39 for 30 mg).

This study incorporates the use of an adaptive design. Adaptive features may be implemented at the discretion of the Investigator to support conduct of the study. Such adaptive features do not require amendment of the protocol. Adaptive features and their limits are described in [Table 4](#).

Table 4. Adaptive Protocol Features

Features	Limits
1. Outpatient Period (Day 9 to Day 23) may be extended up to an additional 14 days with Investigator approval with adequate supply of study intervention to support daily dosing can be provided, and with record of exact duration of Outpatient Period is recorded; participants will reinitiate the study on Day 23.	
 • Not >14 days
2. Participants may be checked in on Day 22 rather than Day 23 at the Investigator discretion.	
 • Check-in to clinical research unit allowed 1 day prior

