Psychiatric assessment	Evidence of clinically significant acute psychiatric worsening which may include but not limited to suicidality, acute depression, or psychosis.		Investigator and Alexion Medical Monitor will evaluate the need for dose modification (interruption, increase or decrease) based on copper control parameters and relevant clinical data. Rationale for dosing decision must be documented in study record and re-evaluated at the next study visit.	Worsening psychiatric symptoms will be documented as adverse events in the eCRF and will be followed until completion of the study or resolution of symptoms.	Discuss with the Alexion Medical Monitor.

^a For changes in safety monitoring, weekly repeat testing for laboratory parameters can be completed by a home healthcare nurse if a routine study visit is not scheduled during this time period.

^b A maximum of 3 rechallenges will be allowed.

^c For rechallenges, participants who were on 15 mg QOD should be rechallenged at the 15 mg QOD dose.

^d The Investigator, in consultation with the Medical Monitor, may change dose and dose frequency in participants who require rechallenge.

Abbreviations: AEs = adverse event; ALT = alanine aminotransferase; eCRF = electronic case report form; QD = once daily; QOD = every other day; ULN = upper limit of normal.

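### A full 14-day outpatient extension leaves 19 to 23 days on 15 mg/day with no scheduled safety laboratory test, instead of 5 to 9

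*Protocol*

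**What the plan says.** Protocol Section 1.3, footnote g, sets the only safety check of the Outpatient Period: "A single outpatient visit or phone call and safety laboratory assessment should occur between Day 14 and Day 18".

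Section 4.1 then says that "the Outpatient Period during Treatment Period 1 may be extended up to an additional 14 days with Investigator approval", and Sections 1.1 and 1.2 repeat this. Extra drug is supplied so that daily dosing continues. Table 4, feature 1, makes the extension conditional on Investigator approval and drug supply, "with record of exact duration of Outpatient Period is recorded; participants will reinitiate the study on Day 23". Neither Table 4 nor footnote g adds a laboratory test, visit or call for the added days.

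Footnote r gives the timing of the next tests: "Laboratory assessment including chemistry, hematology, and coagulation parameters should be performed on Days -8, -1, 8, 23, and 28 only". Footnote c allows return to the unit on Day 22, but procedures still begin on Day 23. The outpatient text messages serve only to confirm that doses were taken.

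On the risk itself, Table 3 (Section 2.3.1) says of dose-dependent ALT and AST elevations: "Generally mild to moderate in severity, asymptomatic and reversible with dose adjustments were reported, usually after 3 - 6 weeks of treatment". The mitigation it names is regular liver function testing. This onset timing is given for transaminases only, not for anemia or leukopenia.

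**The concern.** The outpatient laboratory test is tied to fixed study days, while the period it is meant to cover can be lengthened. When the period is extended, the calendar pauses at nominal Day 23 but exposure continues. The added days fall in the interval that Table 3 gives for the usual appearance of transaminase rises, and the single outpatient sample at Day 14 to 18 comes before that interval opens.

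Because the rises are described as asymptomatic, symptoms are unlikely to reveal them between tests. The ALT rules in Table 7 (Section 6.6), from dose reduction to interruption, act only on a measured value. What is at stake is how long a participant keeps taking 15 mg/day before a reportable rise is seen. The primary endpoint is not affected.

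**Working it through.** The plan states no maximum interval between safety tests, so there is no figure of its own to reproduce. The check is day arithmetic.

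**Inputs**
- Outpatient test: Day 14 to Day 18 (footnote g).
- Next scheduled tests: nominal Days 23 and 28 (footnote r).
- Extension: k added days, 0 to 14 (Section 4.1, Table 4).
- Usual onset of transaminase rises: 3 to 6 weeks (Table 3).

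**Gap to the next scheduled test.** Nominal Day 23 becomes actual Day 23 + k. The gap is (23 + k) − 18 = 5 + k for a Day 18 sample, and (23 + k) − 14 = 9 + k for a Day 14 sample.

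| Added days k | Actual day of nominal Day 23 | Gap, Day 18 sample | Gap, Day 14 sample |
|---|---|---|---|
| 0 | 23 | 5 | 9 |
| 7 | 30 | 12 | 16 |
| 14 | 37 | 19 | 23 |

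At k = 14, nominal Day 28 is actual Day 28 + 14 = 42, and the first 30 mg dose (nominal Day 29) is on actual Day 43.

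**Position in the onset window.** Counting 3 to 6 weeks as actual Days 21 to 42 gives 22 days. Unextended, the first test inside it is on Day 23, after 2 days. Fully extended, it is on Day 37, after Days 21 to 36, which is 16 of 22 days (73%). Counting from completed weeks instead, Days 22 to 43 is again 22 days, and Days 22 to 36 is 15 of them (68%). Either way the first test in the window moves by 14 days. These are shares of calendar days, not of risk.

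**When the extension exceeds the ordinary outpatient spacing.** In the unextended outpatient schedule the longest interval is Day 8 to Day 18, or 10 days. With a Day 14 sample, 9 + k > 10 from k = 2. With a Day 18 sample, 5 + k > 10 from k = 6.

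**Draws needed to stay at 10 days or less.** The number is the gap divided by 10, rounded up, minus 1.
- k = 1 (gap 6 to 10): none.
- k = 7 (gap 12 to 16): one.
- k = 14: one for a gap of 19, two for a gap of 23.

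A single midpoint draw at k = 14 leaves at most 23 / 2 = 11.5 days, so 12 in whole days.

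**The case against.** The strongest reply is that the protocol already gives the Investigator the means to test. Each extension needs Investigator approval, given with the Day 14 to 18 result normally in hand. Footnote d says "Unscheduled study visits may occur at any time during the study", Section 10.2 allows additional tests whenever judged necessary, and the participant may be kept in the unit for safety. ALT above twice the upper limit, MELD above 13 and decompensated cirrhosis are excluded at entry. This reduces the practical risk, but none of it requires a sample. Weekly repeat testing under Table 7 begins only after an abnormal value.

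A second reply concerns the onset window. Table 3 pools ALXN1840 with ammonium tetrathiomolybdate and ties no dose to the timing. In Study WTX101-201, 13 + 9 = 22 of 28 participants were on 30 or 60 mg at Week 24 or last dose, so the timing may partly reflect higher doses. An extended participant also stays on 15 mg until actual Day 42, whereas an unextended one is on 30 mg from Day 29. For a dose-dependent effect, total hepatic risk is therefore not shown to rise. This stands: the finding is about delayed detection, not greater incidence.

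Third, the 10-day benchmark is a choice. The plan sets no maximum, and the schedule has 12 to 16 days between Day 40 and the end-of-study visit at Day 54 ± 2, when some participants could still be on drug. That is fair, and the target should be read as a proposal. It does not account for a gap of 19 to 23 days in a period of mandated daily dosing.

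Finally, optional readmission on nominal Day 22 would bring the participant back on actual Day 36. The laboratory test is still on Day 37.

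**Conclusion.** The concern holds. Followed as written, a full extension lengthens the interval between scheduled safety tests from 5 to 9 days to 19 to 23 days, and moves the first test inside Table 3's onset window from Day 23 to actual Day 37. No provision in either document adds a scheduled test or contact for the added days.

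The consequence is limited. The rises are described as generally mild to moderate and reversible with dose adjustment, and 15 mg is the starting dose. Tests on actual Days 37 and 42 and the Safety Review Committee review come before 30 mg. The gap grows with the length of the extension and does not arise without one; how many of the approximately 10 participants would be extended is not stated. The 68 to 73% figure assumes that Table 3's timing applies at 15 mg/day. This is an inexpensive improvement to consider, not a flaw that undermines the study.

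**What to change.** Add one sentence to Table 4, feature 1, and to footnote g: an extension requires the footnote g contact and safety test to be repeated during the added days, so that no more than about 10 days pass between tests on treatment. If the sponsor prefers one rule for every case, a single draw midway between the footnote g sample and readmission keeps the interval at 12 days or less even at full extension.

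Table 7, footnote a, already provides that "weekly repeat testing for laboratory parameters can be completed by a home healthcare nurse"; the same route would spare participants a journey.

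The cost falls only on extended participants: no draw for a 1-day extension, one at 7 days, and one or two at 14 days, plus a phone contact. The flexibility of the extension and the copper balance collections are unchanged.
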